Effects of Liraglutide on Gastric
Functions and their
Relationship to Weight Loss in
Obesity

NCT# 03523273

October 29, 2020

Title: Effects of Liraglutide on Gastric Functions and their Relationship to Weight Loss in Obesity

Principal Investigator: [name].

Co-Investigators: [name]., Ph.D.; [name].; [name].

Technicians, Coordinators: [name], [name]

Collaborators: [name].

ABSTRACT

Obesity prevalence continues to increase worldwide; 69% of U.S. adults are overweight or obese. Despite advances in understanding obesity pathophysiology, weight loss with current non-surgical treatments (diet and medications) is highly variable, and predictors of weight loss with obesity pharmacotherapy are unknown. In studies funded by RO1-DK67071 in 509 participants, obesity was associated with greater fasting gastric volume, accelerated gastric emptying (solids and liquids), lower postprandial peak plasma PYY, and greater calories consumed to achieve satiation (volume to fullness) and to evoke satiety with an ad-libitum meal. We showed that a short-acting GLP-1 agonist, exenatide, 5µg, SQ, BID for 30 days, delays gastric emptying and induces weight loss. Thus, quantitative gastrointestinal (GI) traits are associated with higher BMI, distinguish obesity phenotypes, and may predict efficacy of obesity drug therapy. In the R56-DK67071-funded pilot randomized, placebo-controlled trial of the longer-acting GLP-1 agonist, liraglutide, 3mg, SQ daily, we showed: (a) feasibility to recruit and randomize, over 8 months, 30 patients into a 4-month study (only 2 dropouts on treatment, to date); (b) safety data in all 30 randomized patients; (c) baseline quantitative traits of gastric emptying of solids and liquids, fasting and postprandial gastric volumes; satiation and satiety data; postprandial plasma incretins (GLP-1 and PYY) in all randomized patients; (d) gastric emptying data at fully escalated dose of liraglutide (weeks 5-6) in 30 patients; (e) repeat measurement (as in c) of quantitative traits at 16 weeks' treatment in 28 patients; (f) monthly weight data for duration on treatment in 28 patients.

Our overall hypothesis is that weight loss with pharmacological agents may be individualized, based on specific abnormalities in quantitative GI traits. We propose a randomized, controlled clinical and pharmacodynamics trial, using a 2-treatment stratified design, to assess the hypothesis that a quantitative trait (gastric emptying rate) can impact the weight loss response among overweight (BMI $\geq 27\text{kg/m}^2$ plus obesity co-morbidities) or obese (BMI $\geq 30\text{kg/m}^2$) patients to treatment with the FDA-approved GLP-1 receptor agonist, liraglutide (dose escalated to maximum of 3mg, SQ, per day for 12 weeks) compared to placebo. Effects will be compared for those with baseline accelerated in comparison with normal gastric emptying.

Our *aims* are: first, to assess the effects of liraglutide, 3mg/day, on gastric motor functions, satiation, satiety, weight loss and incretins; and second, to appraise the association of baseline accelerated gastric emptying on weight loss in response to liraglutide treatment. By measuring quantitative GI traits at baseline and after 12 weeks of liraglutide treatment, we shall further understand the mechanism of action of this GLP-1 agonist. As an exploratory assessment, we shall measure stiffness and fat content of liver at three different time points during the study: baseline, week 8, and week 16 of treatment in the 2 treatment groups.

Significance: Our study addresses the treatment of obesity, introducing an era of individualizing drug therapy for obesity based on quantitative biomarkers. Therefore, it addresses an important public health challenge.

APPROACH: GENERAL METHODS

Overall Design, Randomization and Allocation

We shall perform a placebo-controlled, parallel-group trial of liraglutide for a treatment period of 3 months after achieving the target dose (3mg QD) following dose escalation. All participants will undergo baseline measurements of GI, behavioral and psychological traits. These assessments are needed to evaluate potential confounders that may interact with the effects of liraglutide on the endpoints in these studies. Randomization will be stratified on gender, BMI, and GE of solids (accelerated or normal). Overweight or obese patients with delayed GE of solids will be excluded from the trial with liraglutide, given the theoretical risk of induction of symptomatic gastroparesis as a result of further delay in GE. All patients will be randomized to active drug or placebo. Once participants are randomized, the doses and dose escalation (on active drug) will be the same for all subjects, except for delayed dose escalation in patients who cannot tolerate the standard titration (0.6mg per week). A computer generated randomization schedule generated by the study statistician's office will be submitted to the Mayo Clinic CCaTS Research Pharmacy.

Allocations will be concealed; studies will be blinded until data are transmitted to the statistician for data lock.

Selection of Overweight and Obese Participants

We plan to study a cohort of 112 patients (using 2-treatment stratified design) with BMI >30kg/m² or >27kg/m² with an obesity-related co-morbidity [e.g. type 2 diabetes mellitus (T2DM) on metformin monotherapy or diet alone, hypertension, hyperlipidemia, obstructive sleep apnea]. We have already genotyped and obtained baseline quantitative trait measurements of interest [GE of solids, kcal intake at buffet meal, and glycemia indices in obese patients with hyperglycemia (T2DM receiving metformin)] in almost 500 patients residing within 75 miles of Mayo Clinic in Rochester, MN. Over 80% of these patients reside within 25 miles of Rochester, MN. Anticipating 20% drop out from the study (Lean et al. 2014), we will screen 160 patients to ensure 112 enter the 16 weeks' trial of liraglutide, 3mg SQ daily versus placebo, analyzed using ITT principles.

Inclusion criteria:

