At baseline, we shall also measure gastric volume (fasting and post-300kcal Ensure® drink), satiation (volume to fullness and MTV by Ensure® drink test, that is, the kcal intake under constant nutrient liquid intake 30kcal/min), appetite/satiety (kcal intake at an *ad libitum* buffet meal, which will be summarized henceforth as “satiety”), and plasma GLP-1 and PYY during fasting and at 15, 30, 45, and 90 minutes after the start of ingestion during Ensure® drink test. Further details of these measurements are provided below.

These measurements are essential to **ensure that the study stratifies patients based on GE and appraises the effect of liraglutide on the quantitative traits that impact satiation and satiety.**

Baseline and monthly measurements will be taken of hip-waist ratio, DEXA body composition (only at baseline and end of study), height, weight, blood pressure, pulse, and fasting blood glucose. The monthly measurements will also serve to enhance compliance and ongoing standardization of behavioral treatment.

Standardization of Behavioral Treatment

Under the supervision of [name]., co-investigator and staff behavioral interventionist [as in our behavioral protocols in previous clinical trials (Vazquez-Roque et al. 2007, Grudell et al. 2008)] and in a weight regain intervention (Himes et al 2015), we will standardize for potential differences in behavioral aspects of weight reduction therapy. All participants will be given a standard text (“LEARN” Manual, 10th ed.) for guidance on healthy lifestyle changes (Brownell 2004) and will meet at baseline and approximately weeks 4, 8 and 12 with a behavioral interventionist who has expertise in obesity treatment. Under the guidance of [name], the behavioral interventionists (master’s or doctoral level psychologist, a registered nurse, and a bachelor’s level study coordinator) will provide brief behavioral

counseling for weight management to study participants. Study team members will be trained in behavioral interventions through leading or observed a 12 week clinical weight management group sessions provided by the Department of Psychiatry and Psychology. Upon approval by Dr. [name], these study team members will deliver behavioral interventions independently to active participants of this study. [name] meets with the study interventionists monthly to provide ongoing feedback and guidance.

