- e. **Physical Activity Level** - The four-item **Physical Activity Stages of Change Questionnaire** (Marcus et al. 1982) will be utilized to assess the physical activity level of participants. Mayo Clinic investigators, led by co-investigator [name], have used these items to explore the relationship between quality of life and physical activity in long-term lung cancer survivors (Clark et al. 2008, Solberg Nes et al. 2012).

Study Medication: Liraglutide, a Longer-Acting GLP-1 Receptor Agonist

Introduction: Whereas, liraglutide is approved for the treatment of obesity (or overweight with comorbidities), these data are based on large multicenter studies in which the average weight loss was only about 5.6kg over placebo (mean weight loss from baseline 8.4kg) with 12-56 weeks of treatment (Pi-Sunyer et al. 2015).

[figure not shown]

Figure 6. Effect of liraglutide vs. placebo on weight loss in multicenter study of Pi-Sunyer et al. 2015

Almost 20% of patients treated with liraglutide developed adverse events including acute, severe abdominal pain or acute pancreatitis and, more commonly, nausea and vomiting that led to either discontinuation or failure to reach the full dose of 3mg daily after the first 4 weeks of dose escalation required in the trial. Moreover, another multicenter study showed that liraglutide produced small but statistically significant improvements in several cardiometabolic risk factors compared with placebo (Wadden et al.

2013). Given the fact that the multicenter studies may include nonuniform cohorts (e.g. the Pi-Sunyer study included 191 sites in 27 countries in Europe, North America, South America, Asia, Africa, and Australia), studies that explore MECHANISMS of action of the medication require standardized, validated methods. We propose a single-center study in our lab at Mayo Clinic because of the extensive experience and validation of all the quantitative traits [including one study of 509 participants (Acosta et al. 2015)], ensuring eligibility of participants and characterization of behavioral traits (which are potential confounders. The feasibility of the proposed, unique studies are demonstrated in our preliminary data with liraglutide 3mg.

Prior Reports of Effects of Liraglutide on Gastric Functions Are Inconclusive

(i). Horowitz et al. (2012) showed in patients with T2DM that liraglutide, up to 1.8mg dose, resulted in retardation of liquid GE, since it was measured by plasma acetaminophen method.

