10. **Liver Stiffness and fat content:** We will measure the stiffness and fat content of liver non-invasively using different ultrasound equipment at **baseline, 8 weeks and 16 weeks** in participants who provide informed consent. The GE Logiq E9 and/or the Verasonics scanner will be used to for ultrasound measurements. It is beneficial to test the measurements on different ultrasound scanners to evaluate performance. We will analyze results as we study the patients. Based on the results, we may pick one scanner (either GE or Verasonics scanner) to continue the study. Regardless whether one or two scanners are used, we will keep the ultrasound study time within 30 minutes as stated in the consent form.

General Approach for Statistical Analyses

The analyses will be based on a **2-treatment stratified design** to compare the effects of liraglutide and placebo on *post-treatment gastric functions, satiation, satiety, incretins, body composition and weight loss*; *in addition, the effects of liraglutide will be compared between* patients with (vs. without) the trait of interest (i.e., the strata being accelerated vs. normal GE of solids using the 10th percentile for GE of solids in health). The analyses will use a 2-way analysis of covariance (ANCOVA) model with treatment, the quantitative trait, and a treatment by quantitative trait interaction term.

The sample size is based on the feasibility to perform a 16-week therapeutic trial over 4 years, during which approximately 40 participants completed/ year. Year 5 of the proposed application will be necessary for completion of all trait analyses, and writing manuscripts.

Interim Analysis: As part of an on-going method to compare the effects of medication tested (liraglutide) and placebo, an interim analysis will be conducted when >66% of aim 1 has been reached.

Rationale for Interim Analysis:

a. To assess power of the study based on the actual coefficient of variation as measured in the actual study with >66% completed; this is because the coefficient of variation could be different from the COV used in the a priori power calculation used in development of the protocol.

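### ITT is promised with 20% drop-out expected, but the only stated model has no missing-data method and leaves the monthly weights unused

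*Combined protocol and SAP*

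**What the plan says.** - **Principle and drop-out** (Selection of Overweight and Obese Participants). The planned size is given as "We plan to study a cohort of 112 patients". The same paragraph reads "Anticipating 20% drop out from the study", then "we will screen 160 patients to ensure 112 enter the 16 weeks' trial of liraglutide", and ends with the commitment "3mg SQ daily versus placebo, analyzed using ITT principles".
- **Model** (General Approach for Statistical Analyses). The outcomes are "post-treatment gastric functions, satiation, satiety, incretins, body composition and weight loss". The method is "The analyses will use a 2-way analysis of covariance (ANCOVA) model with treatment, the quantitative trait", plus the treatment-by-trait interaction. There is no term for visit or month.
- **Monthly data** (Baseline Characterization of Secondary Quantitative Traits). "Baseline and monthly measurements will be taken of hip-waist ratio", and weight is on that list. The behavioral-treatment section adds that body weight is recorded at every study visit. DEXA is done only at baseline and end, and the abstract puts the GI traits at baseline and one on-treatment time point.
- **Reasons for stopping** (Study Medication). In earlier multicenter trials, almost 20% of liraglutide patients had adverse events, including "nausea and vomiting that led to either discontinuation or failure to reach the full dose of 3mg daily". No placebo rate is given.
- **What is absent.** The document has no imputation rule, analysis-set definition, missing-data assumption or sensitivity analysis, and nothing on follow-up after treatment stops. Two methodological papers on incomplete trial data are in the reference list, but the text neither cites them nor adopts a method from them.

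**The concern.** An ANCOVA with one outcome per person needs that outcome. With no rule for missing values, standard software omits anyone who lacks it, and the result describes completers rather than everyone randomised. The ITT commitment and the stated method then do not meet.

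A comparison of completers is sound if people leave for reasons unrelated to their weight loss. It can be biased if the relation between leaving and weight loss differs between arms. The second aim, whether baseline accelerated GE changes the weight response to liraglutide, rests on an interaction. That is estimated less precisely than the main effect and has little room for lost data.

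For weight, the trial already collects what is needed to do better. A participant who leaves after month 2 has supplied two post-baseline weights, which a repeated-measures analysis uses and the stated model does not.

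**Working it through.** **1. The plan's own figures.** Inputs: 160 screened, 112 entering, 20% drop-out.
- 112 / 160 = 0.70, a 30% loss.
- 112 / (1 − 0.20) = 140, and 160 × 0.80 = 128.

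Neither calculation links 160 to 112, so the document does not settle whether the 20% falls before or after entry.

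**2. Participants without an end value.**
- If 112 enter and 20% then leave: 112 × 0.80 = 89.6, so about 90 have an end value and about 22 do not.
- If 112 is meant as completers: 140 enter and 140 × 0.20 = 28 have no end value.

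**3. Precision if drop-out is random.** The document gives no alpha, power or SD. Assume two-sided alpha 0.05, 80% power and 1:1 allocation.
- Detectable difference in SD units = (1.96 + 0.84) × √(4/N): 0.53 for N = 112 and 0.59 for N = 90. Power at 0.53 SD falls from 80% to 71%.
- Detectable interaction = (1.96 + 0.84) × √(4/(Nq) + 4/(N(1 − q))), where q is the fraction with accelerated GE (not given). It goes from 1.06 to 1.18 SD at q = 0.5, and from 1.76 to 1.97 SD at q = 0.1.
- Both lose the same factor, √(112/90) = 1.12.

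Monthly weights recover part of this (step 4, random drop-out). For SDs of 4, 6 and 8 kg the standard error falls from 0.84 to 0.80, 1.28 to 1.19 and 1.70 to 1.63 kg, a gain of about 4 to 7%. With no drop-out it would be 0.75, 1.14 and 1.54 kg.

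**4. Possible bias for weight (illustration).** From the Study Medication section: 8.4 kg mean loss on liraglutide and 5.6 kg over placebo, which implies 8.4 − 5.6 = 2.8 kg on placebo. Assumed: 56 per arm, weights at months 1 to 4, correlation 0.85 between adjacent months, SD at month 4 of 4, 6 or 8 kg, and overall drop-out of 20 to 23%. Informative drop-out depends on the last observed weight. There were 1,500 simulated trials per setting, and the completer estimate is the simple difference in mean loss.

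| Drop-out pattern | Completers, SD 4 / 6 / 8 (kg) | Likelihood on all monthly weights (kg) |
|---|---|---|
| Random in both arms | 5.62 / 5.63 / 5.54 | 5.62 / 5.64 / 5.56 |
| Placebo leave after small loss; liraglutide at random | 4.88 / 4.56 / 4.18 | 5.61 / 5.65 / 5.60 |
| As above, and liraglutide leave after large loss | 4.19 / 3.47 / 2.75 | 5.61 / 5.62 / 5.55 |

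Against the full-data means in the second pattern (5.59, 5.64, 5.60 kg), the completer bias is 0.71, 1.08 and 1.42 kg. The arms have equal SDs, so applying the same rule to liraglutide instead of placebo reverses the sign: about 5.6 + 0.7 = 6.3 kg up to 5.6 + 1.4 = 7.0 kg. A second simulation (SD 5 kg, correlation 0.9, about 20% drop-out after month 2, informative in one arm) gave completer estimates from 4.61 to 6.60 kg and likelihood estimates of 5.59 to 5.62 kg.

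**5. What the monthly weights do not settle.** Suppose 20% of the liraglutide arm stop and end with only the placebo loss of 2.8 kg. The effect in everyone randomised is 0.8 × 8.4 + 0.2 × 2.8 − 2.8 = 4.48 kg, against 5.6 kg in completers. If those people were losing weight typically until they left, a mixed model on their earlier weights also returns about 5.6 kg. The 4.48 kg and 5.6 kg figures answer different questions. Reaching the first needs weights after stopping, or an explicit assumption about them.

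**The case against.** The strongest reply is that the plan is silent, not wrong. A reader might infer that it excludes drop-outs or commits to a completer analysis. It says neither: the section is headed as a general approach, and imputation followed by ANCOVA would fit both the ITT commitment and the stated model. That stands, and the defect is an omission.

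A reader might also infer that drop-out will differ by arm. The Study Medication text concerns other trials, gives no placebo rate, and counts people who failed to reach full dose, who may still have an end weight. The pilot had 2 drop-outs among 30, by arm not stated. Differential drop-out is therefore plausible but not shown, and actual loss may be below 20%.

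The simulations rest on assumed SDs, correlations and drop-out rules, and the 5.6 and 8.4 kg inputs come from 12 to 56 weeks of treatment. Drop-out was made to depend on observed weights, which is the condition under which the likelihood analysis is valid. The results show direction and possible size, not a forecast.

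The remedy has limits too. Monthly weights help little if people leave before supplying any; the pilot reports monthly weights for 28 of 30. They give no repeated measure of GE half-time or body composition. Choosing a mixed model over imputation for weight is partly preference.

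What survives is that the document names neither method, and the weights it collects allow a better analysis than the one it states.

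**Conclusion.** The point holds as a gap between the ITT commitment and the stated analysis. Run as written, the ANCOVA can use about 90 of 112 participants if the 20% applies after entry, and it leaves the intermediate weights unused.

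The consequence depends on why people leave. If drop-out is random, the estimate is unbiased; a repeated-measures analysis would shrink the standard error by about 4 to 7% under the assumptions above. If drop-out is related to weight loss differently by arm, the weight-loss and treatment-by-GE comparisons could be biased in either direction.

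Three stronger conclusions are not supported. The documents do not show that the effect will be overstated by 1.1 kg; that figure assumes a particular outcome for those who stop. They do not show that the interaction loses proportionately more than the main effect; both lose the same factor. And a mixed model does not by itself deliver an ITT effect that includes people who stop treatment.

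**What to change.** Before data lock, add the following to the analysis section.

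- **Weight:** a mixed model for repeated measures on all available monthly weights of all randomised participants. Terms: month, treatment by month, GE stratum, treatment by GE stratum by month, baseline weight, and the other randomisation factors (gender and BMI). Report the treatment contrast and the treatment-by-GE interaction at end of treatment.
- **Outcomes measured only at baseline and end** (GE half-time, DEXA and similar): multiple imputation within arm from the baseline value, stratum and monthly weights, with the completer ANCOVA as a sensitivity analysis.
- **Assumptions:** state that the mixed model assumes missing at random. State also that an ITT effect including people who stop treatment uses any weights obtained after stopping or, failing that, an explicit assumption about them in a sensitivity analysis.
- **Counts:** reconcile 160, 112 and 20%, and say whether 112 means entrants or completers.

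The cost is SAP wording and modest programming. Collecting weights after study drug is stopped, where still possible, is a small extra data-collection burden; weights not taken from people who have already left cannot be recovered by rewording the plan.

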g. Intake of any medication (except multivitamins) within 7 days of the study. Exceptions are birth control pill, estrogen and thyroxine replacement therapy, and any medication administered for co-morbidities as long as they do not alter GI motility including GE and gastric accommodation. For example, statins for hyperlipidemia, diuretics, β -adrenergic blockers, ACE inhibitors and angiotensin antagonists for hypertension, and metformin for T2DM or prediabetes are permissible. In contrast, resin sequestrants for hyperlipidemia (Psichas et al. 2012), α 2-adrenergic agonists for hypertension, or other GLP-1 agonists (exenatide) or amylin analogs (pramlintide) or DPP-IV inhibitors are not permissible since they significantly affect gastric functions or appetite.

h. Delayed gastric emptying at 2 and 4 hours

i. Hypersensitivity to liraglutide

j. Participate in highly intense physical activity program that could potentially interfere with study interpretation

Baseline Primary Quantitative Trait Relevant to Effect of Liraglutide: Gastric Emptying

At baseline, **GE of solids** will be measured and participants characterized as having accelerated GE [$T_{1/2}$ of solids <93min in females, <78min in males (Camilleri et al. 2012)] or normal GE (see 10th-90th percentile in **Table 5**). Patients with delayed GE of solids (>90th percentile according to gender) will be excluded, since it is unethical to potentially induce gastroparesis or significantly increase the delay in GE with a GLP-1 agonist in patients with baseline abnormal GE of solids. Note that gender, but not age or BMI, was associated with GE of solids (GE $T_{1/2}$, and proportion emptied at 1h and 2h, all $p < 0.001$) in healthy controls (Camilleri et al 2012).

Table 5. GE in healthy controls using identical method to that in application (Camilleri et al 2012).

Data show mean \pm SD	All controls, n=319	Male controls, n=104	Female controls, n=215
Age, y	36.2 \pm 13.1	34.6 \pm 13.3	37.2 \pm 12.8
BMI, kg/m ²	26.9 \pm 5.1	27.8 \pm 4.5	26.5 \pm 5.3
Solid GE $T_{1/2}$,	121.7 \pm 29.8	109.9 \pm 28.6	127.7 \pm 28.7

Baseline Characterization of Secondary Quantitative Traits Relevant to the Effects of Liraglutide

At baseline, we shall also measure gastric volume (fasting and post-300kcal Ensure® drink), satiation (volume to fullness and MTV by Ensure® drink test, that is, the kcal intake under constant nutrient liquid intake 30kcal/min), appetite/satiety (kcal intake at an *ad libitum* buffet meal, which will be summarized henceforth as “satiety”), and plasma GLP-1 and PYY during fasting and at 15, 30, 45, and 90 minutes after the start of ingestion during Ensure® drink test. Further details of these measurements are provided below.

These measurements are essential to **ensure that the study stratifies patients based on GE and appraises the effect of liraglutide on the quantitative traits that impact satiation and satiety.**

Baseline and monthly measurements will be taken of hip-waist ratio, DEXA body composition (only at baseline and end of study), height, weight, blood pressure, pulse, and fasting blood glucose. The monthly measurements will also serve to enhance compliance and ongoing standardization of behavioral treatment.

Standardization of Behavioral Treatment

Under the supervision of [name]., co-investigator and staff behavioral interventionist [as in our behavioral protocols in previous clinical trials (Vazquez-Roque et al. 2007, Grudell et al. 2008)] and in a weight regain intervention (Himes et al 2015), we will standardize for potential differences in behavioral aspects of weight reduction therapy. All participants will be given a standard text (“LEARN” Manual, 10th ed.) for guidance on healthy lifestyle changes (Brownell 2004) and will meet at baseline and approximately weeks 4, 8 and 12 with a behavioral interventionist who has expertise in obesity treatment. Under the guidance of [name], the behavioral interventionists (master’s or doctoral level psychologist, a registered nurse, and a bachelor’s level study coordinator) will provide brief behavioral

counseling for weight management to study participants. Study team members will be trained in behavioral interventions through leading or observed a 12 week clinical weight management group sessions provided by the Department of Psychiatry and Psychology. Upon approval by Dr. [name], these study team members will deliver behavioral interventions independently to active participants of this study. [name] meets with the study interventionists monthly to provide ongoing feedback and guidance.

The behavioral interventionists will follow a session outline to standardize session content. Study participants will be taught a range of behavioral skills for successful weight management. These will be 15 to 20 minute, standardized counseling sessions that incorporate motivational interviewing strategies. To maintain treatment fidelity, the psychologists will then complete visit forms documenting the content of the completed counseling session. Additionally, study participants will have brief (10min) contact with a member of the study team approximately every 4 weeks to inquire about their adherence to study protocol, any difficulties they are experiencing, whether they are reading the LEARN Manual (**Table 6**), and to answer any additional questions arising from their reading and lifestyle change. At each study visit, adherence to medication intake will be assessed, and body weight and automated blood pressure will be recorded in the Mayo Clinical Research Unit. In previous studies (Levine et al. 2005), we have provided study participants with recognition to demonstrate our appreciation for their time and to reduce study attrition. At week 8, participants will receive a token of thanks (Mayo Clinic water bottle) and at week 16, a copy of the book, The Mayo Clinic Diet.

Table 6. Content of counseling sessions and LEARN Manual assignments

	Discussion and Values	Reading assigned
1	a. introduce the LEARN manual; b. discuss the concept of readiness for change; c. differences between lifestyle change and diet highlighted; d. value of keeping food records, identifying eating triggers, and e. importance of eating 3 scheduled meals per day	chapters 1-4 of the LEARN manual prior to next visit
2	a. review chapters 1-4 of the LEARN manual; b. eating triggers, the benefits of physical activity, and problem solving strategies	chapters 5-8 of the LEARN manual
3	a. review chapters 5-8 of the LEARN manual; b. role of social support for health behavior changes; c. strategies for goal setting and controlled eating	chapters 9-12 of the LEARN manual
4	a. review chapters 9-12 of the LEARN manual, b. review progress in physical activity and meal planning; c. strategies to challenge negative thinking and relapse prevention techniques	

After September 7, 2018, the MAYO CLINIC DIET BOOK will be used exclusively since the LEARN manual is no longer available.

Session	Discussion and Values	Reading assigned
1	Introduce the Mayo Clinic Diet book: Chapter 1, Ready Set Go; Chapter 2, Add Five Habits; Chapter 5, What Have You Learned; Chapter 6, The Next Phase; Chapter 7, Know Your Goals; Chapter 11, Track Your Progress	Chapters 1, 2, 5, 6, 7, 11
2	Review chapters previously assigned: Chapter 3, Break Five Habits; Chapter 4, Adopt Five Bonus Habits; Chapter 10, Expand Your Activity Plan	Chapters 3, 4, 10
3	Review chapters previously assigned: Chapter 8, Set Your Targets; Chapter 9, Create Your Eating Plan; Chapter 12, Seek Support	Chapters 8, 9, 12
4	Review chapters previously assigned: Chapter 13, What's Your Healthy Weight; Chapter 14, Energy Calories and Weight; Chapter 15, The Mayo Clinic Healthy Weight Pyramid; Chapter 16 Making Meals Easier; Chapter 17, Eating Out; Chapter 18, How to Change Behaviors; Chapter 19, Burning Even More Calories; Chapter 20, I Slipped Up-What Do I Do?	Chapters 13-20

Questionnaires to Assess GI Symptoms and Affective Disorders

Participants will complete a series of questionnaires (all included in the APPENDIX): GI symptoms with the validated Bowel Disease Questionnaire (Talley et al. 1989), the Psychosomatic Symptom Checklist to assess the level of somatization, and the Hospital Anxiety and Depression Inventory (Zigmond & Snaith

1983) to appraise the contribution of affective disorder, which may confound assessment of weight effects of liraglutide.

Questionnaires to Exclude Addiction and Psychiatric Eating Disorders (potential confounders of weight effects of liraglutide)

- a. **AUDIT-C Alcoholism Screening Test** (Bush et al. 1998) - The AUDIT-C is a 3-item alcohol screening questionnaire that reliably identifies participants who are hazardous alcohol drinkers or have active alcohol use disorders. This score will be used in screening by the study physician/nurse coordinator. The AUDIT-C is scored on a scale of 0-12. Each AUDIT-C question has 5 answer choices. Points allotted are: a=0 points; b=1 point; c=2 points; d=3 points; e=4 points. In men, a score of 4 or more will be reviewed by study personnel, and in women, a score of 3 or more will be reviewed by study personnel. However, when the points are above recommended limits, the provider will review patient's alcohol intake over past few months to confirm accuracy.
- b. **Eating Disorders Questionnaire - The Questionnaire on Eating and Weight Patterns-5 (QEWP-5, Appendix 7)** (Yanovski et al. 2015) is a valid measure of screening for eating disorders which has been used in its different iterations since 1993 (Yanovski 1993) in several national multi-site field trials. Respondents are classified as binge eating disorder or bulimia nervosa. We have used this instrument to screen for eating disorders in obese populations (Vazquez-Roque et al. 2007). Since the QEWP-5 may not be sufficiently sensitive and specific to rule out binge eating disorder, based on a gold-standard diagnostic interview (de Zwaan et al. 1993), we shall be most careful to rule out binge eating disorder via **clinical interview** (with the expertise of [name]), since this important phenotype has been shown to have an impact on energy intake in laboratory studies (Walsh et al. 2003) and on gastric size (Geliebter et al. 2004). In a community sample, we found an association with binge eating patterns and GI symptoms (Cremonini et al. 2009). We will also administer the QEWP-5 for DSM-5 criteria assessment.
- c. **Body Image Satisfaction - The Multidimensional Body-Self Relations Questionnaire** (Brown et al. 1990) provides a standardized attitudinal assessment of body image, normed from a national body-image survey (Cash et al. 1986). Items are rated on a 5-point scale, ranging from 1=Definitely Disagree to 5=Definitely Agree. In this study, we will use one of the sub-scales, the Body Areas Satisfaction Scale, which measures feelings of satisfaction with discrete aspects of physical appearance (e.g., face, weight, hair). Cronbach's α values range from .70 to .89 (Cash 1994).
- d. **Eating Behaviors - The Weight Efficacy Life-Style Questionnaire** [WEL (Clark et al. 1991; Batsis et al. 2009; Ames et al. 2015)] is a 20-item eating self-efficacy scale consisting of a total score and five situational factors: negative emotions, availability, social pressure, physical discomfort, and positive activities. Subjects are asked to rate their confidence about being able to successfully resist the urge to eat using a 10-point scale ranging from 0=not confident to 9=very confident.
- e. **Physical Activity Level** - The four-item **Physical Activity Stages of Change Questionnaire** (Marcus et al. 1982) will be utilized to assess the physical activity level of participants. Mayo Clinic investigators, led by co-investigator [name], have used these items to explore the relationship between quality of life and physical activity in long-term lung cancer survivors (Clark et al. 2008, Solberg Nes et al. 2012).

Study Medication: Liraglutide, a Longer-Acting GLP-1 Receptor Agonist

Introduction: Whereas, liraglutide is approved for the treatment of obesity (or overweight with comorbidities), these data are based on large multicenter studies in which the average weight loss was only about 5.6kg over placebo (mean weight loss from baseline 8.4kg) with 12-56 weeks of treatment (Pi-Sunyer et al. 2015).

[figure not shown]

Figure 6. Effect of liraglutide vs. placebo on weight loss in multicenter study of Pi-Sunyer et al. 2015

Almost 20% of patients treated with liraglutide developed adverse events including acute, severe abdominal pain or acute pancreatitis and, more commonly, nausea and vomiting that led to either discontinuation or failure to reach the full dose of 3mg daily after the first 4 weeks of dose escalation required in the trial. Moreover, another multicenter study showed that liraglutide produced small but statistically significant improvements in several cardiometabolic risk factors compared with placebo (Wadden et al.

2013). Given the fact that the multicenter studies may include nonuniform cohorts (e.g. the Pi-Sunyer study included 191 sites in 27 countries in Europe, North America, South America, Asia, Africa, and Australia), studies that explore MECHANISMS of action of the medication require standardized, validated methods. We propose a single-center study in our lab at Mayo Clinic because of the extensive experience and validation of all the quantitative traits [including one study of 509 participants (Acosta et al. 2015)], ensuring eligibility of participants and characterization of behavioral traits (which are potential confounders. The feasibility of the proposed, unique studies are demonstrated in our preliminary data with liraglutide 3mg.

Prior Reports of Effects of Liraglutide on Gastric Functions Are Inconclusive

(i). Horowitz et al. (2012) showed in patients with T2DM that liraglutide, up to 1.8mg dose, resulted in retardation of liquid GE, since it was measured by plasma acetaminophen method.

(ii). Rotondo et al. (2013) showed that 0.6mg liraglutide had no effects on gastric perception, compliance or satiation, but it inhibited gastric accommodation measured by balloon in 10 healthy controls with normal BMI.

(iii) Van Can et al. (2014) studied effects of once daily liraglutide, 1.8mg, 3.0mg, or placebo, in a double-blind, incomplete crossover, 5-week trial on GE, glycemic parameters, appetite and energy metabolism in obese, non-diabetic adults. They showed reductions in 1-hour GE of 23% with liraglutide, 3.0 mg, and 13% with 1.8mg compared to placebo. Given the method used to measure GE (plasma acetaminophen), the study could only appraise GE of liquids, and the effect of the GLP-1 agonist was only demonstrable in the first hour. It is not surprising that the 5-hour AUC was not different between liraglutide and placebo, since, over that period, all the acetaminophen should be emptied from the stomach and absorbed in the normal small bowel.

Thus, prior PUBLISHED studies are inconclusive, and effects of 3mg liraglutide on GE solids in short term (5 wk) and at 16 wks were unknown, other than the preliminary data from our pilot study.

Approval status by FDA (December 23, 2014): Liraglutide is indicated as an adjunct to a reduced-calorie diet and increased physical activity for chronic weight management in adults with BMI of ≥ 30 kg/m² (obesity) or a BMI of ≥ 27 kg/m² (overweight) with ≥ 1 weight-related condition (e.g., hypertension, T2DM, dyslipidemia).

Dosing recommendations: Initiate at 0.6mg S.C. daily for 1 week; increase by 0.6mg/day in weekly intervals until a dose of 3mg/day is achieved.

Supply: Liraglutide (3mg SQ injection) and placebo will be dispensed by Mayo Clinic Research Pharmacy. As in the pilot study, all supplies will be dispensed by the pharmacy staff at a site away from the Clinical Research Unit and the study staff.

Randomization: The randomization schedule will be generated before the start of the study in the Section of Biostatistics, Mayo Clinic, and will be given to the research pharmacist. Medications will be stored in a

monitored, climate-controlled environment according to manufacturer's directions. Monitoring records will be available for review to ensure quality control.

